7.7.2. Secondary outcomes

7.7.2.1. *Medication adherence* will be assessed by medication refill adherence (MRA) (Hess et al., 2006) in week 16. A systematic review of current or recently used measures of calculating adherence from administrative data recommended MRA as the preferred measure of adherence, because of its convenience while still produces equivalent results comparing with other measures (Hess et al., 2006). Pharmacy dispensing data (Merlin) will be used to determine MRA, defined as the total days' supply divided by the number of days of study participation and multiplied by 100. Data will be extracted at a single time point once the last patient has reached week 16. Data will be extracted by pharmacy as part of collaboration in this research program. Note that the total days' supply will include any deliberate break periods, e.g. if the patient is asked to take the drug for 21 days, follows by 7 days break, then the total days' supply will be 28. If the patient needs to reduce the dose for some medical reasons, e.g. side effects, the MRA formulation will be manually adjusted accordingly. In this study, the patient will be considered as optimal adherence if their MRA is $\geq 90\%$.

Note that MRA may be impacted if patients are given larger pack sizes and therefore not coming in at every cycle or if dose adjustments occur due to toxicity resulting in a participant using a single pack for longer. Therefore, the RC will collect this information and compare the MRA with patients' responses to drug reminders on the SAMSON mobile app and discuss with the PI case by case.

7.7.2.2. *Self-report adherence* will be measured by ASK-12 (Matza et al., 2009) at weeks 1 and 12. This instrument was originally designed with 20 questions to provide a practical, yet detailed, assessment of adherence behaviour as well as potential barriers to adherence (Hahn et al., 2008). The ASK-20 has been used in studies focusing on a range of treatments and settings, for example asthma and different pharmacy programs. The shorter refined version of this instrument, i.e. ASK-12 includes 12 items in three sub-scales: adherence behaviour, health beliefs and inconvenience or forgetfulness. The tool has good internal consistency reliability (Cronbach alpha = 0.75) and test-retest reliability (intraclass correlation = 0.79). This tool was found to be practical and useful for the

Pilot Randomized Controlled Trial Study Protocol
Version 1.0 – 2 May 2023, Amendment 1 dated 26 June 2023

clinical setting for predicting risk of nonadherence as well as measuring rates of adherence (Matza et al., 2009; Spoelstra & Rittenberg, 2015). Completion of the ASK-12 is anticipated to take approximately 2-3 minutes.

7.7.2.3. Toxicity Self-management will be assessed at week 1 and week 12: Patient Activation Measure-Short Form (PAM-SF) (Hibbard et al., 2005) is a 13-item self-report measure assessing the patient's knowledge, skills, and confidence in the self-management of their disease and related symptoms. Responses to each of the 13 items are measured using a 4-point Likert scale, with responses ranging from 1 (strongly disagree) to 4 (strongly agree), with an additional 'not applicable' option. Scores range from 0-100, which categorise patients into one of four possible groups: (1) disengaged and overwhelmed, (2) becoming aware but still struggling, (3) taking action, and (4) maintaining behaviours and pushing further. Higher scores are reflective of greater activation. This scale has good internal consistency, $\alpha = 0.81$ (Prey et al., 2016). Completion of the PAM-SF is anticipated to take approximately 5-10 minutes.

7.7.2.4. Anxiety, Depression and Symptoms will be assessed at week 1 and week 12: Patient-Reported Outcomes Measurement Information System (PROMIS) scales – adult short-form will be used to assess **depression** (4-items), **anxiety** (4-items), **pain interference** (4-items), **fatigue** (4-items), **sleep disturbance** (4-items) and **physical function** (6-items). These self-report scales have excellent test-retest reliability ($\geq .86$) and acceptable convergent and discriminative validity in people with cancer (Quach et al., 2016). PROMIS encompasses a set of person-centred measures that evaluate and screen for dysfunction in physical, mental, and social health in children and adults. PROMIS utilises a T-score metric with a mean of 50 and a standard deviation of 10 in a reference population. Higher scores on the PROMIS scales are indicative of a higher degree of the concept being measured, with a score range of 20-80. For mental health, pain, and sleep scales, higher scores indicate greater dysfunction. For the physical function scale, higher scores indicate lower dysfunction. Completion of the PROMIS scales (26 items in total) is anticipated to take approximately 5-10 minutes.

7.7.2.5. Quality of Life will be assessed at week 1 and week 12: Functional Assessment of Cancer Therapy-General (FACT-G) (Cella et al., 1993) is a 27-item self-report scale measuring quality of life of patients currently undergoing cancer treatment. Questions are categorised according to measurement domain, which are: physical wellbeing (7-items), social/family wellbeing (7-items), emotional wellbeing (6-items), and functional wellbeing (7-items). The response format for all questions is a 5-point Likert scale ranging from 0 (not at all) to 4 (very much), with higher scores indicative of a better state of health. The scale has shown internal consistency of $\alpha \geq .90$ overall and $\alpha \geq .70$ for each subscale, and acceptable convergent validity when assessed in patients with non-Hodgkin's lymphoma (Yost et al., 2013). Completion of the FACT-G is anticipated to take approximately 5-10 minutes.

7.7.2.6. Optimal intervention strategy: will be measured by qualitative questions in the UTAUT surveys for both clinicians and patients at week 12 to identify the optimal dose of delivering MI tele-consultations.

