7.2. Number of participants and study duration

Thirty to fifty patients will be recruited into the pilot RCT. The study will run for 16 weeks. During this 16-week, the patient in the intervention arm will:

- have access to the SAMSON mobile app (the first component of the intervention solution) throughout the study period, and
- receive initial pharmacist consultation and tele-consultations provided by their care team at Peter Mac, i.e nurses or pharmacists, in weeks 1, 4, 8 and 12.

All randomisations will be done by the study statistician.

Recruitment will be undertaken over a period of 6 months and the intervention is expected to be completed in ten months from recruitment commencement.

The patient in the controlled arm will receive usual care at the hospital (see details in section 7.9.2).

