7.6. Study population

7.6.1. Inclusion criteria

All the following criteria must be satisfied for enrolment in the study.

- 1) A confirmed diagnosis of any-stage haematological, lung or melanoma cancer;
- 2) Scheduled to commence oral anti-cancer medicine(s) as part of routine care or commencing treatment/currently treated with the medication for less than 12 months;
- 3) Willing to have oral anti-cancer medicine(s) dispensed at Peter Mac;
- 4) Over 18 years old;
- 5) Proficient in English; and
- 6) Accessibility to the internet, a smartphone (and computer), and/or telehealth.

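### The refill-adherence formula ignores supply left over at the end and supply held at entry, so the 90% cut does not work at 90% and treats new and existing users differently

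*Protocol*

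**What the plan says.** Section 7.7.2.1 names the source, "Pharmacy dispensing data (Merlin) will be used to determine MRA", and the formula, dispensed days' supply "divided by the number of days of study participation and multiplied by 100". The classification rule is also fixed there: "the patient will be considered as optimal adherence if their MRA is" 90% or more. Two adjustments are given: planned treatment breaks count as supplied days (the example is 21 days on and 7 off, counted as 28), and dose reductions lead to a manual change. Data are extracted once, after the last patient reaches week 16.

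The section concedes part of the problem: "Note that MRA may be impacted if patients are given larger pack sizes", or if a dose change makes one pack last longer. Its remedy is that the research coordinator collects this information, compares MRA with responses to the app's reminders, and discusses cases individually with the principal investigator.

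On the window, section 7.2 says "The study will run for 16 weeks", and the synopsis gives the same length for each patient. On the population, section 7.6.1 admits patients scheduled to start an oral anti-cancer medicine as well as those "commencing treatment/currently treated with the medication for less than 12 months".

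**The concern.** Supply enters the numerator when it is dispensed, while the denominator is time in the study. The two match only if supply dispensed in the window is also meant to be used in the window. Two things break this. The last dispensing may reach well past week 16 and is still counted in full. An existing user may enter with drug at home, and that supply counts for nothing. The first overstates adherence, most clearly in new starters. The second lowers the score of some existing users. Without a cap, values above 100% also enter the mean.

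MRA is the first secondary outcome and the only adherence measure that is not self-reported. Section 7.10 plans between-group comparisons and will use the results to choose endpoints and size the larger trial. A misplaced cut and an artificial SD would carry over into that design.

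**Working it through.** The protocol gives no numerical result for this outcome to reproduce. Its one worked figure, 21 + 7 = 28 days' supply, is correct. The check applies the formula as written.

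**Inputs from the protocol.** Window 16 × 7 = 112 days; cut 90%, that is 0.90 × 112 = 100.8 days' supply; 28 days' supply per cycle in its example.

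**Assumptions.** Each fill supplies s days (14 to 84); true adherence a is steady; patients refill only when stock runs out; existing users hold h days of supply at entry, spread evenly over 0 to s − 1.

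**Formula.** Fills fall on days h/a, (h + s)/a, (h + 2s)/a and so on. With k fills before day 112, MRA = 100 × s × k / 112.

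**New starters (h = 0).** To reach 90%, the k-th fill must fall before day 112, so a must exceed (k − 1) × s / 112.

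| Days per fill | Fills needed for 90% | MRA then scored | True adherence that passes |
|---|---|---|---|
| 14 | 8 | 100% | above 98/112 = 88% |
| 21 | 5 | 93.8% | above 84/112 = 75% |
| 28 | 4 | 100% | above 84/112 = 75% |
| 30 | 4 | 107.1% | above 90/112 = 80% |
| 56 | 2 | 100% | above 56/112 = 50% |
| 84 | 2 | 150% | above 84/112 = 75% |

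**Existing users, 28-day fills, a = 80%.** Fills are 28/0.8 = 35 days apart. Four fit only if the first falls in days 0 to 7, so 7/35 = 20% pass (6 of 28 = 21% over whole-day stock values). The rest score 84/112 = 75%. A new starter with the same behaviour always scores 100%. Over whole-day stock values, existing users pass in 43% at a = 85%, 61% at a = 90% and 82% at a = 95%; new starters pass in 100% at each.

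**Spread.** If every existing user truly takes 80%, scores are 75% with probability 0.8 and 100% with probability 0.2. The mean is 0.8 × 75 + 0.2 × 100 = 80, and the SD is 25 × √(0.8 × 0.2) = 10 points, with no true variation.

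**Fully adherent existing users.**
- 30-day fills: the fourth fill falls on day h + 90, before day 112 only if h is below 22. The other 8 of 30 values (27%) score 90/112 = 80.4%.
- 84-day fills: the second fill falls on day h + 84, before day 112 only if h is below 28. The other 56 of 84 values (67%) score 75%; the rest score 150%.
- 14-, 21-, 28- or 56-day fills with less than one pack in hand: none fail. With exactly one full 28-day pack in hand, the score is 84/112 = 75%.

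**Early leaver.** A new starter withdrawn on day 30 after two 28-day fills scores 56/30 = 187%.

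**After correction** (days with drug on hand, entry stock credited, cut at the end of participation, capped):
- New starter, a = 80%, 28-day fills on days 0, 35, 70 and 105: (3 × 28 + 7)/112 = 81%, against 100%.
- Existing user, a = 80%, h = 14, fills on days 17.5, 52.5 and 87.5: (14 + 28 + 28 + 24.5)/112 = 84.4%, against 75%.
- Fully adherent existing user, 30-day fills, h = 25: (25 + 30 + 30 + 27)/112 = 100%, against 80.4%.
- The leaver on day 30: 100%, against 187%.

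**The case against.** The strongest reply is that truncation, carry-in and capping are programming conventions that an analysis plan may settle, and that the protocol adopts a measure recommended by the review it cites. This stands only in part. The protocol itself fixes both formula and cut, and followed as written they misclassify patients.

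The second reply is stronger: the sizes rest on refill at run-out. Section 7.7.2.1 speaks as if attendance at each cycle were usual. If patients collect on days 0, 28, 56 and 84 whatever they have left, a new starter at 80% scores 112/112 = 100% on both the present and the corrected measure, and the gain disappears. That stands. Pack sizes are also unstated; counting by whole pack is inferred from the use of dispensing records.

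Third, the plan has safeguards: pack-size and dose information is collected, and cases are reviewed. But the review compares MRA with app responses, and under section 7.9.2 control patients have no access to the intervention. The app check can therefore correct only the intervention arm, and no rule governs it. Supply held at entry is not mentioned.

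Three stronger readings are not supported. A reader might infer that the 90% rule acts everywhere as 75%; the table shows 50% to 88%, depending on fill size. A reader might expect scores of 125% with 28-day fills; under refill at run-out a fifth fill never falls before day 112. A reader might conclude that the formula biases the comparison of arms. Section 7.5 randomises 1:1 in blocks of 4, so the mix of users is balanced on average, and existing users' mean MRA is close to the truth (80.4% at a = 80% with 28-day fills, over whole-day stock values).

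**Conclusion.** The concern holds in this form: the definition is badly fixed. Under refill at run-out, new starters pass the 90% rule at true adherence as low as 50% to 88%, depending on fill size. Existing users are misclassified according to how much drug they hold at entry; fully adherent ones fail only with some pack sizes (30- and 84-day fills among those checked).

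The formula alone mainly adds non-differential noise. With 30 to 50 patients and no stated stratification, a chance imbalance in user type is possible, but it is not a systematic bias. The more certain cost is to the SD and the endpoint choice passed to the full trial. A difference between arms could enter through the app-based review. MRA is a secondary, mainly descriptive outcome with no feasibility threshold in Table 1, so this should be corrected but does not threaten the pilot's primary aims.

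**What to change.** Replace the formula in section 7.7.2.1 with the percentage of days in the window with drug on hand, from the same dispensing source:
- Start at the later of randomisation and first dispensing.
- Carry in unused supply from the last dispensing before entry where it is recorded; otherwise start at the first in-study dispensing or flag the patient.
- Cut supply at the end of participation, and cap at 100%.
- Apply the 90% cut to this value, by the same rule in both arms and without app responses.

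The cost is revised wording, an extract that looks back before enrolment, and a little more programming. Carry-in will be incomplete for patients previously dispensed elsewhere, since section 7.6.1 asks only for willingness to have medicines dispensed at the study hospital. Residual error remains near the cut (a new starter at 89% on 28-day fills scores 90.7%), with long packs (existing users at 80% on 84-day fills score 80% to 95%), and where patients collect by cycle regardless of remaining stock. These limits should be stated with the results.

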Usual care	
The usual care often includes:
 
 - An initial pharmacist consultation for medication reconciliation and medication dispensary consultation, contraindications, adverse drug reactions, administration instructions for each medication schedule, and address any patient concerns. - A consultation with the clinic clinician, to provide education about medication, and patient-focused management of side-effects. The clinic nurse will be the patient's ongoing contact for the management of any side-effects related to their treatment medication. - Telephone follow-up, provided by the oncology nurse, within 1-2-week time if no risk/need for earlier support is required. If the oncology nurse identifies there might be a need of extra support, the patient will be followed up with a telephone call within a few days. If a patient displays a high level of competence and no concerns during their education session, they will not be followed up. Instead, they will be asked to call or email the oncology nurse if required.
Measures	
Patient-reported outcome measures will be administered via REDCap, a secure online data collection tool, via email or in hard copies. All study measures administered are reliable and valid (see section 7.3 for more details).
 
Primary 1- Acceptability will be measured by a questionnaire, guided by the Unified Theory of Acceptance and Use of Technology (UTAUT) at week 12
 
Primary 2- Feasibility will be measured both quantitatively and qualitatively throughout the study, including recruitment, randomisation, retention, intervention adherence, and assessment processes. For intervention patients, responses to weekly side effects surveys and daily medication reminders will also be measured.
 
Secondary 1- Medication adherence will be measured by medication refill adherence (MRA) at week 16.
 
Secondary 2- Self-report adherence will be measured by ASK-12 at weeks 1 and 12
 
Secondary 3- Toxicity Self-management will be measured by the Patient Activation Measure-Short Form (PAM-SF) at weeks 1 and 12
 
Secondary 4- Anxiety, Depression and Symptoms will be measured by PROMIS scales at weeks 1 and 12

Pilot Randomized Controlled Trial Study Protocol
Version 1.0 – 2 May 2023, Amendment 1 dated 26 June 2023

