7.5. Randomisation and allocation procedures

- Following consent, the study statistician (CI [name]), located at Swinburne University, will randomise participants 1:1 in blocks of 4 to intervention or usual care arms and send by email to the RC who will arrange participants to the arm specified in the email.
- All participants will be asked to provide their contact details for communication during the study and be provided with a unique identifying number and link to the online questionnaires to be completed within three days of consenting to participate in the trial. This set of questionnaires include: PAM-SF, PROMIS, FACT-G, and ASK-12 (Attachment 2). Participants can select the questionnaires in hard copy if they wish to.
- The RC will follow-up with participants to ensure questionnaires are completed. Following completion of the above questionnaires, the research assistant will advise the participant which study arm they were randomised to.
- If randomised to the intervention, participant patients will:
 - Be provided with the SAMSON mobile app user manual (Attachment 3a) to install the SAMSON mobile app onto their smartphone. They will also be given a password and username to access the SAMSON system. The RC will assist to download the APP and train them in how to use the SAMSON APP and webpage.
 - Receive an initial pharmacy consultation with the SAMSON trained pharmacist following the intervention manual (Attachment 4a). This consultation will be conducted either face-to-face, via phone or online.
 - Have their medication reminders and side effects surveys programmed into the app.
- Participants randomised to the control arm will be provided with pharmaceutical care as usual.

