7.8. Intervention

The SAMSON (Safety and Adherence to Medications and Self-care advice in Oncology) intervention solution, is the next iteration of the REMIND intervention. REMIND was developed and assessed in 10 patients with CML. Results of the REMIND trial have been published:

Pilot Randomized Controlled Trial Study Protocol
Version 1.0 – 2 May 2023, Amendment 1 dated 26 June 2023

SAMSON is a digital support tool used in conjunction with usual care to improve adherence, reduce administration and interaction errors, and provide evidence-based advice for effective management of medication side-effects. It includes two elements:

- 1) SAMSON mobile app, including smartphone-based app to remotely prompt MA, monitor patient side-effects and deliver self-care advice; and computer-based app to enable adherence and side-effect reporting. The beta-version of SAMSON mobile app has been tested on 30 people with haematology cancer at Peter Mac in 2021 (HREC/74134/PMCC). Data on patient's diagnosis and treatment will be extracted from the patient's medical record at PeterMac. Data on drug administration, indications, cautions and side-effects, and counselling have been developed by Peter Mac Pharmacy Medicines Information Service, based on approved product and consumer information resources (Appendix 1). Self-care advice information has been developed based on resources such as American Society of Clinical Oncology (ASCO), Cancer Australia, Health Direct and Peter Mac's information for patients and carers, and reviewed by the SAMSON clinical team (Appendix 2). All data will be entered into the SAMSON platform by the RC. Drugs names and dosages will be matched with the patient's prescription; thus the patient will only receive prompted reminders and feedback on medication adherence status relating to their own treatment. Examples of how this information is shown in the SAMSON app are in Appendix 3. The project team member will debrief study nurses and pharmacists on how to use the SAMSON webpage at the beginning of the study, and continue providing IT support for them if issues arise.

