7.9.2. Patients randomised to the controlled arm

- Participants in the control/usual care arm will receive usual care and will not have access to any of the intervention. Standard care will involve:
 - A consultation in the clinic with the clinic clinician, to provide education about medication, and patient-focused management of side-effects including the appropriate action to take regarding serious side-effects (e.g. when/where to seek urgent medical attention). The disease stream nurse will be the patient's ongoing contact for the management of any side-effects related to their treatment medication.
 - An initial pharmacist consultation at Peter Mac for the patient who chooses to fill their prescription at Peter Mac. In this consult, a medication reconciliation and medication dispensary consultation is conducted with a pharmacist to catalogue the patient's prescription and non-prescription medications (including new medications), identify any contraindications, adverse drug reactions, provide administration instructions for each medication schedule, confirm that administration instructions have been understood, and address any patient concerns regarding their medication or medication schedules.
 - Follow-up after commencing medication will be undertaken within 1-2-weeks by the disease stream nurse for assessment of early toxicity.
- Patients are provided with the contact details for the pharmacist and disease stream nurse, and can call or email if required, although they are advised of the limitations of this (i.e. business hours) and to seek alternative/urgent medical assistance if required outside of business hours.

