9.3. Monitoring and project governance

This study will be coordinated centrally by the research team based at Peter Mac Parkville. PI [name] will maintain regular weekly contact with the RC to ensure that the study is running smoothly, and that recruitment is on target. Adherence to the research protocol will be monitored by the study's Steering Committee throughout the study. Protocol violations or operational issues will be discussed and resolved at project team meetings.

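### The check on distorted refill adherence uses app responses that only the intervention arm has, made by a coordinator who knows the allocation, and nothing stops it altering the outcome

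*Protocol*

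**What the plan says.** MRA is a secondary outcome. Section 7.7.2.1 derives it from pharmacy dispensing data in both arms, as total days' supply over days of study participation times 100, and counts a value of 90% or more as optimal adherence.

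The section makes two provisions for values that may mislead:

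- **Dose reduction for medical reasons:** "the MRA formulation will be manually adjusted accordingly". This is not limited to one arm.
- **Pack size and dose adjustment:** "Note that MRA may be impacted if patients are given larger pack sizes and therefore not coming in at every cycle", or if a toxicity-related dose change makes one pack last longer. As a consequence, the coordinator collects this information, compares MRA with the patient's "responses to drug reminders on the SAMSON mobile app and discuss with the PI case by case".

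Reminder responses belong to one arm. The synopsis (Measures) says: "For intervention patients, responses to weekly side effects surveys and daily medication reminders will also be measured". Section 7.9.2 says that control patients "will receive usual care and will not have access to any of the intervention".

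On who knows the allocation, section 7.5 has the statistician randomise and "send by email to the RC who will arrange participants to the arm specified in the email". Section 7.8 adds: "All data will be entered into the SAMSON platform by the RC". Under section 9.3 the PI "will maintain regular weekly contact with the RC". No masking of the coordinator or the PI is described.

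**The concern.** Pack-size and dose-change artefacts can arise in either arm, because the same pharmacy supplies both. The case-by-case comparison meant to deal with them can be carried out in only one. If its result feeds back into a patient's MRA or adherence category, the outcome is measured differently in the two arms, by someone who knows which arm is which.

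The comparator is also a poor one for this purpose. Under section 7.9.1 it consists of Yes or No taps in reply to a prompt, which is the behaviour the intervention is designed to produce. Table 1 already uses response to reminders as a measure of intervention adherence. The other adherence outcome, ASK-12, is self-reported, so MRA is the one adherence outcome that does not rest on self-report. Letting app responses influence it would weaken that independence in one arm.

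What is at stake is the adherence part of the potential-efficacy objective (section 6) and the use of the results for endpoint selection and sample size in a larger trial (section 7.10). The primary outcomes, acceptability and feasibility, are not affected, and no threshold in Table 1 uses MRA.

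**Working it through.** The protocol gives no figure to reproduce: the sample size is pragmatic, and no expected MRA or effect size is stated. The check therefore traces the text and then illustrates the size.

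**Tracing the text**

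| Step | Intervention arm | Control arm |
|---|---|---|
| MRA from dispensing data (7.7.2.1) | yes | yes |
| Manual adjustment for dose reduction (7.7.2.1) | yes | yes |
| Collection of pack-size and dose-change information (7.7.2.1) | yes | yes |
| Comparison with app reminder responses (7.7.2.1; synopsis, Measures; 7.9.2) | yes | not possible |
| Substitute check | not needed | none described |

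The imbalance lies only in the fourth row. Even in the intervention arm, the comparison may not span the whole MRA period: the synopsis lists reminder responses for weeks 1 to 12, while MRA is assessed at week 16.

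**Weight of one patient**

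With 30 to 50 patients randomised 1:1 (sections 7.2 and 7.5), there are about 15 to 25 per arm. One patient moved across the 90% cut-off shifts the arm's optimal-adherence rate by 100/n points:

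- n = 15: 100/15 = 6.7 points
- n = 25: 100/25 = 4.0 points

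**Illustration of a one-directional shift**

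The assumptions here are not in the protocol. There is no true effect, a share p has MRA of at least 90% in both arms, and a fraction q of the intervention arm's remaining patients is moved up because of the app comparison, with no such move in controls. The false difference is (1 − p) × q.

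- p = 0.7, q = 0.3: 0.3 × 0.3 = 0.09, or 9 points (79% against 70%). That is 0.09 × 15 = 1.35 patients, or 0.09 × 25 = 2.25 patients.
- p = 0.8, q = 0.2: 0.2 × 0.2 = 0.04, or 4 points.
- p = 0.6, q = 0.5: 0.4 × 0.5 = 0.20, or 20 points.

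**If moves go both ways**

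Let r be the fraction of the intervention arm's patients at or above 90% who are moved down because of No or missing taps. The net shift is (1 − p) × q − p × r. At p = 0.7 and q = 0.3 it is zero when r = 0.09/0.7 = 0.13 and negative beyond that. The sign depends on how cases are judged, and the protocol gives no rule for that.

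**Against random error**

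The 95% half-width for a difference between two proportions is 1.96 × √(2p(1 − p)/n). At p = 0.5 this is 35.8 points with 15 per arm and 27.7 with 25; at p = 0.8 it is 28.6 and 22.2. A 9-point shift is therefore smaller than the sampling error. Unlike sampling error, it does not average out, and it would carry into any planning value taken from the pilot.

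**The case against.** The strongest objection is that the text says compare and discuss, not correct. A reader might infer that MRA is adjusted differently in the two arms, but the protocol does not say this. The step could be a validity check on a known weakness of refill data, which suits a pilot meant to inform the choice of endpoints. This stands, and it limits the finding to what the procedure permits. Even so, the step is introduced as the response to distorted MRA, and nothing in the section says that the value stays as it is.

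Other limits also stand:

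- **Dose reductions.** The manual adjustment applies in either arm and is not evidence of a between-arm difference.
- **Direction.** A reader might assume that the bias favours the intervention. Patients can tap No, and Table 1 allows for incomplete response, so a high MRA from a large pack could be judged down.
- **The PI.** The coordinator's knowledge of allocation is stated. The PI's is inferred: seeing app responses in a case discussion reveals the arm.
- **Size.** The fraction q is applied to every patient below 90%, but only those with large packs or dose changes would be reviewed. Their share is unknown, and q could be close to zero.
- **Detail left to the SAP.** The lack of a derivation rule for a secondary outcome is not itself a fault, since an SAP that is not shown may hold one. That does not answer the point, because the protocol itself prescribes a check that can be run in only one arm.

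**Conclusion.** The concern holds in limited form. The protocol sets out an unmasked, case-by-case check on MRA that can be made only in the intervention arm, and leaves open whether its result may change the outcome. If it does, the between-arm MRA comparison is biased, with a sign and size that the documents do not determine.

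The figure that depends on the fewest assumptions is 6.7 to 4.0 points per patient reclassified. The 9 points, and the range of 4 to 20, rest on assumed adherence and reclassification rates and on all moves being upward. They show what is possible and are not estimates.

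This should be fixed, but it does not threaten the trial: MRA is a secondary outcome in a mainly descriptive pilot. The documents do not support saying that MRA is corrected only in the intervention arm, or that a gain for the intervention is built in.

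**What to change.** Amend section 7.7.2.1, and carry the same wording into the SAP, as follows:

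1. State that app reminder responses do not alter any patient's MRA value or adherence category.
2. Handle pack size and dose changes in both arms by one written rule that uses only dispensing and prescription records, applied to a file without arm labels.
3. Report the unadjusted MRA beside the adjusted one, so that the effect of the adjustments is visible in each arm.
4. Report app responses, and their agreement with MRA if wanted, separately as a descriptive measure in the intervention arm.

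The first item alone closes the main gap. The others guard against the same problem entering through unmasked manual adjustment.

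The cost is a change of wording and minor work to mask the arm in the pharmacy extract, which is already planned as a single extraction. The real loss is that app information can no longer help to resolve an individual doubtful case.
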